5.2. Primary Outcome

• Treatment success rate at 24 months after the initiation of treatment:

- ‘Cured’ and ‘treatment completed’ are defined as treatment success, and ‘culture’ defined below refers to results of liquid culture.
- Treatment failure, death, loss to follow-up, transfer out and relapse were excluded from treatment success.
- Definitions of treatment outcomes refer to 2014 WHO Guidelines (20). However, ‘stopping’ of drugs during treatment will not be considered as ‘drug change’ (Please see ‘6 Definitions’ in this protocol below.).

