8.3. Baseline Visit and Beginning of Treatment

- AFB smear microscopy, and MTB culture on liquid and solid media of sputum or bronchoscopic specimen will be performed.
- CXR, ECG, complete blood count, electrolytes, chemistry (albumin, total bilirubin, alkaline phosphatase, AST, ALT, Creatinine), anti-HIV antibody and HBsAg will be performed.
- Ishihara Test for Color-blindness will be performed to check baseline abnormalities of color blindness.

* Tests could be skipped in case of having available results or tests were performed recently within four weeks (In case of ECG, within a week).

* Study drugs can be administered before the obtaining of anti-HIV Ab, HBsAg, and alkaline phosphatase results since eligibility is not determined by these results.

* Administration of anti-TB regimen can begin at baseline visit since drug-resistant TB must be treated immediately.

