8.4.2. Follow-up visits after EOT (Investigational arm only)

- Sputum AFB smear microscopy and MTB culture on liquid and solid media
- CXR

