3.2 Handling of Missing Data

When categorized as 'loss to follow-up', 'withdrawal', or 'withdrawal of consent' will be considered as below.

- ① 'Treatment failure' in the case of dropping out due to 'loss to follow-up', 'investigator's decision', 'withdrawal of consent', 'treatment failure', or 'death' during the treatment
- ② 'Not accessible' in the case of dropping out due to 'pregnancy' during the treatment
- ③ 'Treatment failure' in the case of dropping out due to 'relapse' after the treatment completion. However, reinfection by other strain is 'not assessable'.
- ④ 'Not accessible' when there is no evidence of treatment failure, such as bacteria reversion in the case of withdrawal due to 'loss to follow-up', 'investigator's decision', 'withdrawal of consent', 'pregnancy', or 'death' after the treatment completion

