- In order to test whether there is a statistical difference in sputum culture conversion proportions at six months of the treatment between the control arm and the investigational arm (liquid and solid culture media), each arm is summarized by conversion frequency and proportion, and the sputum culture conversion proportion at six months between the two arms are compared using the Chi-square test and Fisher's exact test.

4) Proportion of Treatment Success at the End of Treatment

- Summarize the frequency and proportion of treatment success at the end of Treatment in the investigational arm.

5) Proportion of Relapse after Treatment Success

- Summarize the frequency and proportion of relapse after the treatment success in the investigational arm.

Relapse is defined as mycobacterium tuberculosis (MTB) is cultured again at least two or more consecutive times, taken at least 4 weeks apart, after treatment success (excluding re-infection confirmed by other strains).

6) Proportion of deaths and Time-to-Death

- Summarize the frequency and proportion of death in the investigational arm and estimates the median survival time using the Kaplan-Meier method.

7) Primary Outcome Evaluation Between Treatment Groups According to the Pyrazinamide Resistance

- Presentation of treatment success rate in the control arm and the investigational arm in small groups according to the presence or absence of Pyrazinamide resistance, and verification of non-inferiority of treatment success rate difference between the treatment groups.

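### Relapse is defined only by two positive cultures, and the plan does not say how a participant who restarts TB treatment after completion without a second positive is scored in the primary outcome

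*Combined protocol and SAP*

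**What the plan says.** Protocol 5.2 makes relapse part of the primary outcome: "Treatment failure, death, loss to follow-up, transfer out and relapse were excluded from treatment success". The protocol's definitions section does not define relapse. The SAP does so once, under the secondary outcomes in 3.6.2 item 5: the organism must be "cultured again at least two or more consecutive times, taken at least 4 weeks apart, after treatment success", "excluding re-infection confirmed by other strains".

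SAP 3.2 governs participants who leave after completing treatment. Item 3 assigns "Treatment failure' in the case of dropping out due to 'relapse' after the treatment completion", and makes re-infection by another strain not assessable. Item 4 assigns 'Not accessible' "when there is no evidence of treatment failure, such as bacteria reversion in the case of withdrawal" for several reasons, investigator's decision among them. SAP 3.6.1 then excludes 'Not accessible' participants from the primary evaluation.

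The neighbouring definitions do not fill the gap. Reversion (protocol 6.3 and the notes to 6.4) also needs two positive cultures. Treatment failed (protocol 6.4) concerns treatment terminated or a regimen changed, not treatment restarted after completion.

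Visits after end of treatment (EOT) are two-monthly (protocol 8.4). Protocol 8.4.2 is headed "Follow-up visits after EOT (Investigational arm only)" and lists smear, culture and chest X-ray. Note 7 to the schedule in protocol 7.2 drops the check of other medication after EOT.

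**The concern.** Take a participant in the investigational arm who completes treatment, has one positive culture at a follow-up visit, and is put back on TB treatment. If the next culture is negative, the relapse definition is not met. The same holds for someone re-treated on clinical or X-ray grounds with no positive culture. No rule in either document classifies the restart itself.

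Two outcomes other than failure are then open. A participant who stays in follow-up can remain a success. A participant withdrawn by investigator's decision can be read as 'Not accessible', because the only evidence of failure that item 4 names is reversion, itself a two-positive event. Failure is certain only if the drop-out is labelled as relapse, and the trial is open-label.

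The exposure is lopsided. Before month 24 the investigational arm has 24 - 12 = 12 to 24 - 9 = 15 months off treatment. The control arm has 24 - 24 = 0 to 24 - 20 = 4. A missed recurrence therefore raises the investigational success rate or shrinks that arm's denominator. Both favour non-inferiority, and lasting cure is what a shortened regimen has to show.

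**Working it through.** **Inputs.** From protocol 10.1 and SAP 2.3.1: control 80%, investigational 90%, margin -0.10, one-sided alpha 0.025, power 80%, 48 evaluable per arm, inflation by 0.50 x 0.95. The plan does not name its interval method, so a Wald interval is assumed. The share of the arm re-treated without a second positive is not in the documents; a range of 1-5% is assumed.

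**The plan's own figure.** n = [0.80 x 0.20 + 0.90 x 0.10] x (1.960 + 0.842)^2 / (0.90 - 0.80 + 0.10)^2 = 0.25 x 7.849 / 0.04 = 49.06, rounded up to 50. This is within 2 of the stated 48, and power at 48 per arm is 79.1%. The inflation 48 / (0.50 x 0.95) = 101.05, rounded up to 102, matches. The sample size is not at issue here.

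**One participant.** Lower limit = (pT - pC) - 1.960 x sqrt[pT(1 - pT)/nT + pC(1 - pC)/nC], with control 39/48 = 81.25%:

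| Scoring of one re-treated participant | Investigational | Difference | SE | Lower limit | Against -10% |
|---|---|---|---|---|---|
| Non-success | 41/48 = 85.4% | 4.2 | 7.60 | -10.7% | not shown |
| Excluded | 41/47 = 87.2% | 6.0 | 7.45 | -8.6% | non-inferior |
| Success | 42/48 = 87.5% | 6.3 | 7.38 | -8.2% | non-inferior |

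Exclusion moves the difference by 1.8 points and success by 1/48 = 2.1 points. These counts were chosen to lie near the margin. A second pair behaves the same way: with control 38/48, 40/48 gives -11.4%, 40/47 gives -9.4% and 41/48 gives -9.0%.

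**Error rate at the margin.** Set true success at 80% and 70%, with 48 per arm. Let a fraction m of the investigational arm be true failures re-treated without a second positive, and none in control. Counted as successes, the apparent rate is 0.70 + m; excluded, it is 0.70/(1 - m). The exact columns give the binomial probability that the Wald limit exceeds -0.10.

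| m (assumed) | As success, normal approximation | As success, exact | Excluded, exact |
|---|---|---|---|
| 0 | 2.5% | 2.7% | 2.7% |
| 1% | 3.2% | 3.5% | 3.3% |
| 2% | 4.2% | 4.5% | 4.0% |
| 3% | 5.3% | 5.8% | 4.7% |
| 5% | 8.5% | 9.1% | 6.8% |

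For m = 2% as success: SE = sqrt(0.80 x 0.20/48 + 0.72 x 0.28/48) = 0.0868; z = (0.72 - 0.80 + 0.10)/0.0868 - 1.960 = -1.73; probability 4.2%. Scoring these participants as non-success returns the rate to the m = 0 row.

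**The case against.** The two-culture rule is a defensible choice. It mirrors the protocol's definition of reversion and protects against a single contaminated or isolated positive. It also sits under outcomes described as exploratory.

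The text leaves room for the right answer. The words 'such as' in item 4 are illustrative, so one positive followed by re-treatment could be taken as evidence of failure. 'Cured' and 'Treatment completed' both require no evidence of failure, and a participant withdrawn because the organism regrew fits item 3 naturally. All of this stands. It shows that a sensible analyst could score the case as failure, not that the plan requires it.

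Three stronger readings are tempting, and the documents do not support them.

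- A reader might infer that the plan says restarting treatment does not count. It is silent on the matter.
- A reader might infer from "drug-resistant TB must be treated immediately" that re-treatment routinely follows one positive culture. That is a note in protocol 8.3 on why the regimen may begin at the baseline visit; it says nothing about recurrence.
- A reader might combine the two-monthly visits, an assumed 2-6 week reporting lag and the three-month conversion rates of an earlier trial (88.3% and 90.5%, protocol 3.1) to claim that 36-70% of relapses would give a negative second culture. This needs every relapse to be re-treated on one positive, no sputum before the restart, and exponential clearance in a different population. With a lag of 4-6 weeks, a sputum taken at the restart would already be at least 4 weeks after the first, and the definition is not limited to scheduled visits.

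On data capture, SAP 6.4 does summarise concomitant medication over the study period, so restarts are not necessarily lost. They are just not a scheduled item after EOT.

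**Conclusion.** The point holds as a gap in the primary outcome. Relapse decides success, its only definition needs two positives at least 4 weeks apart, and a restart of TB treatment after completion without a second positive has no assigned score. Success and exclusion are both open readings, and the resulting error would fall almost wholly in the investigational arm, towards non-inferiority.

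The size per participant is firm at 48 per arm: about 2 points, enough to change the conclusion near the margin. The rise in one-sided error from about 2.5-2.7% to about 4.2-4.5% is conditional on 2% of the investigational arm being miscounted as successes, none in control, and a Wald interval. No frequency of relapse or re-treatment can be taken from the documents, so the total effect is unknown.

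**What to change.** In the primary outcome definition and SAP 3.2 items 3 and 4, score any restart of TB treatment after EOT for recurrent TB as non-success, in either arm, with or without a second positive culture. State in item 4 that such a restart is evidence of failure. Keep the existing exception: re-infection confirmed by another strain stays not assessable. Align the matching rules in protocol 10.2, which lack that exception.

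Add one case report form item at each post-EOT visit: TB treatment restarted, date, reason. Leave the two-culture relapse rate unchanged as the secondary outcome, and repeat the primary analysis under the two-culture definition as a sensitivity analysis.

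The cost is a few lines of text and one form item. The drawback is that a few participants re-treated on an open-label decision, without proven relapse, would count as non-success, mostly in the investigational arm. That works against the new regimen; the sensitivity analysis shows by how much. The change concerns outcome scoring only, not when anyone is treated.

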3.7 Safety Analysis

The safety analysis evaluates subjects enrolled in this clinical trial and administered the study drug at least one time.

1) Adverse Events

- The analysis obtains the 95% confidence interval of the proportion of the subjects who have experienced one or more adverse event within each arm and performs the Chi-Square Test or Fisher's Exact Test to compare the treatment groups.
- It compares the occurrence rate of adverse drug reactions of the two arms using the Chi-square test or Fisher's exact test.
- It summarizes the number of adverse events of each arm.
- It summaries the number of expressions of five items (seriousness, severity, relation, action taken, and outcome) for each arm.
- The classification of adverse events by body system is organized according to the SOC (System Organ Class) and PT (Preferred Term) of MedDRA system.
- It describes the details such as demographic information, event date, end date, severity, relation, action taken, and outcome for the subjects who reveal serious adverse events.

2) Physical/Neurological Examination Result

- For the results of the physical/neurological examination, the analysis presents the proportion of subjects who were normal in screening visit (Visit1) and changed to abnormal at the final visit.

3) Chemistry/Electrolyte/Complete Blood Count Result

- The analysis presents the proportion of subjects who showed the chemistry/electrolyte/complete blood count result of "Normal" or "Abnormal NCS" at the baseline visit (Visit2) and changed to "Abnormal CS" at the final visit.

4) Concomitant Medication

- The analysis classifies the concomitant medication using the ATC (Anatomical Therapeutic Chemical)

Code presents it for each arm.

4. Subjects

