7.1. Control arm

	Screening	Baseline Visit ¹	Treatment						End of Treatment ⁷	End of Study
Weeks (w)	-2w ~ 0d	0	1w	2w	4w	8w	12w~ (Every 4w)	52w~ (Every 2month)	80w~	24month
Visit window	n-a	n-a	±4d	±4d	±1w	±2w	±2w	±2w	±2w	±2w
Consent	O									
Randomization		O								
Medical history	O									
Physical Exam	O		O	O	O	O	O	O	O	O
Neurologic exam	O									
Sputum AFB smear	O ⁵	O ⁵	O	O	O	O	O	O	O	O
TB culture (solid)	O ⁵	O ⁵	O	O	O	O	O	O	O	O
TB culture (liquid)	O ⁵	O ⁵	O	O	O	O	O	O	O	O
Genotypic DST	If available									
Phenotypic DST ²	With first/reverted cultured M.TB									
Chest X-ray (CXR)	O ⁵	O ⁵	O ⁸	O ⁸	O	O	O	O	O	O
Chemistry, Electrolyte	O ⁵	O ⁵	O	O	O	O	O	O	O	
Complete blood count	O ⁵	O ⁵	O	O	O	O	O	O	O	
ECG	O ⁵									
Urine HCG ³	O	O								
HIV, HBV ⁴		O ⁵								
Optic test	O									
Compliance of drug intake			O	O	O	O	O	O	O	
Adverse drug reaction			O	O	O	O	O	O	O	
Other medication ⁶	O	O	O	O	O	O	O	O	O	

¹Administration of anti-TB regimen can begin at baseline visit since drug-resistant TB must be treated immediately.

²Drug susceptibility test for isoniazid, rifampicin, ethambutol, pyrazinamide, streptomycin, kanamycin, amikacin, capreomycin, ofloxacin, levofloxacin, moxifloxacin, prothionamide, cycloserine, and para-aminosalicylic acid (omit for patients with results already provided).

³Only for childbearing age (the blood HCG test result can be extracted)

⁴Study drugs can be administered before the obtaining of results since eligibility is not determined by these results.

⁵Could be skipped if previous tests except ECG were done within four weeks. In case of ECG, within 1week.

⁶Check prohibited drugs for exclusion criteria at screening visit, and check immunosuppressants including steroids after enrollment.

⁷End of treatment(EOT) visit will be determined by the standard TB treatment guidelines. If EOT visit and the end of study(EOS) visit are the same, a test corresponding to the EOT visit will be conducted.

⁸Could be skipped if previous CXR test was performed within 2 weeks

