7.2. Investigational arm

	Screening	Baseline Visit ¹	Treatment					End of Treatment ⁷	Treatment completion to End of Study
Weeks (w)	-2w ~ 0d n-a	0 n-a	1w	2w	4w	8w	12w ~ (Every 4w)	40w ~ 52w	~ 24month (Every 2month) ±2w
			±4d	±4d	±1w	±2w	±2w	±2w	
Consent	O								
Randomization		O							
Medical history	O								
Physical Exam	O		O	O	O	O	O	O ⁷	
Neurologic exam	O		O	O	O	O	O	O ⁷	
Sputum AFB smear	O ⁵	O ⁵	O	O	O	O	O	O	O
TB culture (solid)	O ⁵	O ⁵	O	O	O	O	O	O	O
TB culture (liquid)	O ⁵	O ⁵	O	O	O	O	O	O	O
Genotypic DST	If available								
Phenotypic DST ²	With first/reverted cultured M.TB								
LZD, Delamanid resistance examination	If needed (please see the protocol section 9.0)								
Chest X-ray (CXR)	O ⁵	O ⁵	O ⁸	O ⁸	O	O	O	O	O
Chemistry, Electrolyte	O ⁵	O ⁵	O	O	O	O	O	O ⁷	
Complete blood count	O ⁵	O ⁵	O	O	O	O	O	O ⁷	
ECG	O ⁵	O ⁵	O	O	O	O	O	O ⁷	
Urine HCG ³	O	O	O	O	O	O	O	O ⁷	
HIV, HBV ⁴		O ⁵							
Optic test	O	O	O	O	O	O	O	O ⁷	
Compliance of drug intake			O	O	O	O	O	O ⁷	
Adverse drug reaction			O	O	O	O	O	O ⁷	
Other medication ⁶	O	O	O	O	O	O	O	O ⁷	

¹Administration of anti-TB regimen can begin at baseline visit since drug-resistant TB must be treated immediately.

²Drug susceptibility test for isoniazid, rifampicin, ethambutol, pyrazinamide, streptomycin, kanamycin, amikacin, capreomycin, ofloxacin, levofloxacin, moxifloxacin, prothionamide, cycloserine, and para-aminosalicylic acid (omit for patients with results provided already).

³Only for childbearing age (the blood HCG test result can be extracted).

⁴Study drugs can be administered before the obtaining of results since eligibility is not determined by these results.

⁵Could be skipped if previous tests except ECG were been done within four weeks. In case of ECG, within 1week.

⁶Check prohibited drugs for exclusion criteria at screening visit, and check immunosuppressants including steroids after enrollment.

⁷End of treatment visit will be determined by the time of culture conversion. Omit test after end of treatment (EOT) visit.

⁸Could be skipped if previous CXR test was performed within 2 weeks

Confidential

MDR-END v14.0, 20Mar2020

8. Screening and Procedures

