Plain chest PA is performed per routine diagnostic method at each site. If possible, below conditions will be followed: 120kV, tube current (in milliamperes) with automatic exposure control, and a 12:1 antiscatter grid with a 180-cm focus-detector distance.

7) HIV, HBV Test

Peripheral blood 5mL is collected in plain tube and ELISA performed to detect anti-HIV antibody, HBs Ag.

8) Complete Blood Count

Peripheral blood 3mL is collected in EDTA tube to test red blood cell count (RBC), mean corpuscular volume (MCV), white blood cell count (WBC) with differential count, hemoglobin, hematocrit, and platelet count.

9) Chemistry

Peripheral blood 3mL is collected in SST tube to test total bilirubin, albumin, alkaline phosphatase, AST, ALT, Creatinine, and electrolytes examination.

10) Urine HCG Test

Confidential

MDR-END v14.0, 20Mar2020

Urine 10-50mLs collected to test pregnancy by human chorionic gonadotropin (β -hCG) determination kit.

11) Color vision test

Identify number of plates accurately read using the Ishihara Test for Color Blindness (24 plates).

12) Electrocardiography

Measure QT interval.

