6.2 Physical/Neurological Examination Result

For the results of the physical/neurological examination, the analysis presents the proportion of subjects who were normal at Screening visit (Visit1) and changed to abnormal at End of Study (Table 28).

Table 28. Physical/Neurological Examination Result

Investigational arm (N=xx)		Control arm (N=xx)	
n (%)	Normal → Abnormal, n (%)	n (%)	Normal → Abnormal, n (%)
mITT			
Physical examination	xx	xx (xx.xx)	xx
Neurological examination	xx	xx (xx.xx)	xx
PP			
Physical examination	xx	xx (xx.xx)	xx
			xx (xx.xx)

Neurological examination	xx	xx (xx.xx)	xx	xx (xx.xx)
Safety				
Physical examination	xx	xx (xx.xx)	xx	xx (xx.xx)
Neurological examination	xx	xx (xx.xx)	xx	xx (xx.xx)

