6.3 Chemistry/Electrolyte/Complete Blood Count

The analysis presents the proportion of subjects who showed the chemistry/electrolyte/complete blood count result of “Normal” or “Abnormal NCS” at Baseline visit (Visit2) and changed to “Abnormal CS” at End of Study (Table 29).

Table 29. Chemistry/Electrolyte/Complete Blood Count

	Investigational arm (N=xx)		Control arm (N=xx)	
	n	Normal or Abnormal NCS → Abnormal CS, n (%)	n	Normal or Abnormal NCS → Abnormal CS, n (%)
mITT				
Chemistry				
T-bilirubin	xx	xx (xx.xx)	xx	xx (xx.xx)
Alkaline phosphatase	xx	xx (xx.xx)	xx	xx (xx.xx)
AST	xx	xx (xx.xx)	xx	xx (xx.xx)
ALT	xx	xx (xx.xx)	xx	xx (xx.xx)
Creatinine	xx	xx (xx.xx)	xx	xx (xx.xx)
Albumin	xx	xx (xx.xx)	xx	xx (xx.xx)

Electrolyte

Sodium	xx	xx (xx.xx)	xx	xx (xx.xx)
Potassium	xx	xx (xx.xx)	xx	xx (xx.xx)
Chloride	xx	xx (xx.xx)	xx	xx (xx.xx)

Complete blood count

WBC	xx	xx (xx.xx)	xx	xx (xx.xx)
ANC	xx	xx (xx.xx)	xx	xx (xx.xx)
Hemoglobin	xx	xx (xx.xx)	xx	xx (xx.xx)
PLT	xx	xx (xx.xx)	xx	xx (xx.xx)

PP**Chemistry**

T-bilirubin	xx	xx (xx.xx)	xx	xx (xx.xx)
Alkaline phosphatase	xx	xx (xx.xx)	xx	xx (xx.xx)
AST	xx	xx (xx.xx)	xx	xx (xx.xx)
ALT	xx	xx (xx.xx)	xx	xx (xx.xx)
Creatinine	xx	xx (xx.xx)	xx	xx (xx.xx)
Albumin	xx	xx (xx.xx)	xx	xx (xx.xx)

Electrolyte

Sodium	xx	xx (xx.xx)	xx	xx (xx.xx)
Potassium	xx	xx (xx.xx)	xx	xx (xx.xx)
Chloride	xx	xx (xx.xx)	xx	xx (xx.xx)

Complete blood count

WBC	xx	xx (xx.xx)	xx	xx (xx.xx)
ANC	xx	xx (xx.xx)	xx	xx (xx.xx)
Hemoglobin	xx	xx (xx.xx)	xx	xx (xx.xx)

PLT	xx	xx (xx.xx)	xx	xx (xx.xx)
Safety				
Chemistry				
T-bilirubin	xx	xx (xx.xx)	xx	xx (xx.xx)
Alkaline phosphatase	xx	xx (xx.xx)	xx	xx (xx.xx)
AST	xx	xx (xx.xx)	xx	xx (xx.xx)
ALT	xx	xx (xx.xx)	xx	xx (xx.xx)
Creatinine	xx	xx (xx.xx)	xx	xx (xx.xx)
Albumin	xx	xx (xx.xx)	xx	xx (xx.xx)
Electrolyte				
Sodium	xx	xx (xx.xx)	xx	xx (xx.xx)
Potassium	xx	xx (xx.xx)	xx	xx (xx.xx)
Chloride	xx	xx (xx.xx)	xx	xx (xx.xx)
Complete blood count				
WBC	xx	xx (xx.xx)	xx	xx (xx.xx)
ANC	xx	xx (xx.xx)	xx	xx (xx.xx)
Hemoglobin	xx	xx (xx.xx)	xx	xx (xx.xx)
PLT	xx	xx (xx.xx)	xx	xx (xx.xx)

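### SAP 6.2 and 6.3 read Tables 28 and 29 at End of Study, where the investigational arm has no laboratory test or examination scheduled, and one late reading misses on-treatment toxicity that has resolved

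*Combined protocol and SAP*

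**What the plan says.** Two parts of the SAP describe the same two tables and place the later reading differently.

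- **Laboratory results (Table 29).** SAP 3.7, item 3, counts participants who were "Normal' or 'Abnormal NCS' at the baseline visit (Visit2) and changed to 'Abnormal CS' at the final visit". SAP 6.3 gives the later reading as "at End of Study (Table 29". The only transition column in the shell is "Normal or Abnormal NCS → Abnormal CS, n" (%).
- **Physical and neurological examination (Table 28).** SAP 6.2 presents "the proportion of subjects who were normal at Screening visit (Visit1) and changed to abnormal at End of Study". SAP 3.7, item 2, has the same rule but names the final visit.

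The protocol fixes when these measurements are taken.

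- **Investigational arm (7.2, footnote 7):** "Omit test after end of treatment (EOT) visit". Section 8.4.2 lists only sputum tests and chest X-ray for visits after EOT.
- **Control arm (7.1):** the "Chemistry, Electrolyte" row is marked through EOT and blank at End of Study. Footnote 7 adds: "If EOT visit and the end of study(EOS) visit are the same, a test corresponding to the EOT visit will be conducted".

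The documents do not expand CS and NCS. I take them to mean clinically significant and not clinically significant.

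**The concern.** Tables 28 and 29 are the only planned post-baseline summaries of laboratory and examination results. In an open-label trial they are the one check on adverse event reporting that draws on test results rather than on the decision to report an event. Protocol 5.6.3 gives reason to want that check. It lists low hemoglobin, thrombocytopenia, leukopenia and neutropenia for linezolid, and hypokalemia as very common for delamanid.

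Three things weaken it. The visit named in SAP 6.2 and 6.3 is one at which the investigational arm is not tested. A single reading at the end cannot show an abnormality that appeared during treatment and cleared. And the counting rule has no place for a participant who is already CS at baseline and gets worse.

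**Working it through.** The plan states no figure on this point, so there is none to reproduce. The check sets the table rules against the visit schedule.

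**1. Where the measurements are scheduled**

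| Measurement | Control arm (protocol 7.1) | Investigational arm (protocol 7.2) |
|---|---|---|
| Chemistry, electrolytes, blood count | Screening, baseline, treatment visits, EOT; End of Study blank | Screening, baseline, treatment visits, EOT; none after |
| Physical examination | Screening, treatment visits, EOT, End of Study | Screening, treatment visits, EOT; none after |
| Neurological examination | Screening only | Screening, treatment visits, EOT; none after |

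Read at End of Study, Table 29 has no scheduled investigational value. It has control values only where EOT and End of Study are the same visit, which 20 to 24 months of treatment (protocol 5.1.2) allows. In Table 28, physical examination has scheduled End of Study data in controls only, and the neurological row has none in either arm.

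**2. Distance from the last investigational test to End of Study**

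EOT is week 40 or 52 (protocol 8.4). Taking 24 months as about 104 weeks, 104 − 52 = 52 weeks and 104 − 40 = 64 weeks.

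**3. What the count can show, even with data present**

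- On the scale Normal < NCS < CS there are three worsening moves: Normal to NCS, Normal to CS, NCS to CS. Table 29 counts two of the three. A participant who is CS at baseline can never be counted.
- On normal < abnormal there is one worsening move, and Table 28 counts it.
- Either count requires the abnormality to be present at the single later reading. A potassium value that is CS at week 8 and normal at EOT is not counted. Linezolid is given at 600 mg for the first two months and 300 mg afterwards, and may be interrupted for adverse events (protocol 5.1.2), so effects that resolve are plausible.
- The eligibility limits in protocol 5.5 cover 8 of the 13 Table 29 parameters: bilirubin, AST, ALT, creatinine, albumin, WBC, ANC and hemoglobin. Alkaline phosphatase, sodium, potassium, chloride and platelets have no limit.

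**4. Scheduled draws, if the window becomes first dose through EOT (protocol 8.4)**

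- Through week 40: weeks 1 and 2, then every 4 weeks from 4 to 40, so 2 + 10 = 12.
- Through week 52: 2 + 13 = 15.
- Controls to month 20: 15 + 4 = 19. To month 24: 15 + 6 = 21.

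The investigational arm therefore has 12 to 15 draws and controls 19 to 21. To show what this could do to a worst-value table, assume a chance p per draw of a one-grade change unrelated to arm, independent between draws. The chance of at least one in k draws is 1 − (1 − p)^k.

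| Draws k | p = 1% | p = 2% |
|---|---|---|
| 12 | 11% | 22% |
| 15 | 14% | 26% |
| 19 | 17% | 32% |
| 21 | 19% | 35% |

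The values of p are assumptions, not figures from the documents. Through week 40 both arms have 12 draws and this difference disappears.

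**The case against.** The strongest reply is that this is loose wording in a table shell. SAP 3.7 says final visit, which can be read as the last visit with a result. An analyst finding no investigational laboratory data after EOT would use the last available value. That is likely, but it is not what SAP 6.2 and 6.3 say. The choice should be made in the plan rather than at programming, and a last-value reading would still miss resolved toxicity.

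A reader might infer that neither arm has laboratory tests at End of Study. The documents do not support that: control footnote 7 orders the EOT tests when the two visits coincide, although they do not say how often that will happen. Physical examination is also scheduled at End of Study in controls, so that half of the comparison works as written.

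A reader might also infer that counting only new CS results is an error. It is not. Reporting newly significant abnormalities is a legitimate descriptive choice, and leaving out Normal to NCS is defensible. Nor would a fuller normal/abnormal cross-table in Table 28 help those abnormal at screening, because it cannot separate stable from worse. Table 6 already gives the number abnormal at screening.

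Finally, worsening has another planned route. Protocol 11.1 includes worsened severity and abnormal laboratory findings among adverse events, 11.2 requires all of them to be recorded, and SAP 6 grades them by CTCAE v4.0 for Tables 23 to 27. This stands, and it keeps the point minor. What remains is that this route depends on the event being reported.

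**Conclusion.** The point holds as a mismatch between the SAP and the schedule. Table 29 as written in SAP 6.3 has no scheduled investigational data, the neurological row of Table 28 cannot compare the arms, and one late reading is a poor summary of on-treatment toxicity.

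Severity is minor. The number of participants affected cannot be computed, because the documents give no proportion abnormal or CS at baseline. The eligibility limits, and the exclusion of prior optic or peripheral neuropathy, reduce that group without emptying it. It would be too strong to say that the safety comparison fails: the grade 3 or higher adverse event comparison and the efficacy result do not use these tables.

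The conclusion rests on reading End of Study as the 24-month visit, as the protocol schedules do. The remedy also assumes that numeric laboratory values after baseline are held in the CRF. The SAP shows numeric summaries only for screening and baseline (Table 10).

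**What to change.** 1. In SAP 3.7, 6.2 and 6.3, replace final visit and End of Study with one on-treatment window, after first dose through EOT. Define baseline as the last value before first dose, since footnote 5 of both schedules lets the baseline-visit tests be skipped.
2. In Table 29, for each parameter with a CTCAE v4.0 grade, tabulate baseline grade against worst on-treatment grade by arm, from the numeric values. Show each direction separately where a parameter is graded both ways. For ungraded parameters, print the full Normal/NCS/CS shift.
3. Repeat Table 29 through week 40, when both arms have 12 scheduled draws.
4. Give the number tested per arm and parameter. Protocol 8.4.1 lists neither electrolytes nor albumin for controls on treatment, whereas the schedule in 7.1 has an electrolyte row and 8.5 item 9 has chemistry "test total bilirubin, albumin, alkaline phosphatase, AST, ALT, Creatinine, and electrolytes examination".
5. In Table 28, count any abnormal result through EOT among those normal at screening, and mark the neurological row as investigational arm only. Physical examination follows the same treatment visits as the draws, so a week-40 version suits it too.

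The cost is SAP wording and table programming. No new tests are needed if the post-baseline values, and any site reference ranges that grading requires, are in the CRF; otherwise they must be retrieved. The main downside is that controls have more draws through EOT (19 to 21 against 12 to 15), which the week-40 version addresses. Worsening within one CTCAE grade, or within abnormal in Table 28, is still left to the adverse event record.
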